## 15.0 Data handling and record keeping

#### 15.1 Source data and source documents

Source documents include (but are not limited to): the patients' medical records, ECG printouts, laboratory reports, biopsy results, x-ray reports, patient questionnaires, and source data worksheets (which should be filed in the patient's medical records).

Direct access to source data will be granted to authorised representatives from the sponsor, host institution, and the regulatory authorities to permit study-related monitoring, audits, and inspections.

Each centre will be required to complete a Source Data Location agreement as part of the site initiation process in order to confirm the Source Data Locations for the assessments within the protocol.

#### 15.2 Case Report Forms (CRFs)

Data collection will be in the form of completing electronic CRFs via the trial database to record all the required assessments at each study visit. The site study site team should aim to complete the CRF for each visit within one week of the visit date.

Please refer to the Database specification for all values collected within the eCRF, based on the Schedule of Assessments Table.

#### 15.3 Data capture

Source data must be documented on source documents, such as source data worksheets, verified/signed lab reports or x-ray reports, medical notes and patient questionnaires. From these source notes, data is transcribed to the electronic database. When a participant is consented to the trial, the original consent form should be kept in the Investigator Site File, whilst a copy of the consent form should be given to the participant and a further copy should be kept in the participant's clinical notes/folder.

Each patient, at the time of consent, will be allocated a unique screening number by the database before undergoing any screening procedures. This information should be kept on a screening log, which should be updated accordingly throughout the study. Once the patient has completed screening procedures and is enrolled on the study, the patient will be allocated a randomisation number by the trial database.

Appropriate access to the database will be granted only to persons on the delegation log including central coordinating centre at EMR, each local site, and the Sponsor. Access levels will be granted in accordance with the staff members' delegated duties.

Regular data cleaning will be performed by the Coordinating centre to ensure the validity and quality of the data (please refer to the Data Management Plan for full details). An audit trail will be maintained in the database. Study site staff will be trained on the database at the Site Initiation Visit. There is also an e-CRF instruction manual. Study site training should be documented in the Site Initiation Report, and/or in training logs.

The eCRF will be encrypted at the point of the service user and will not provide identifiable data (only year of birth and initials) to the sponsor. The database will be hosted in the Bart's Cancer Institute, QMUL ITS Safe Haven datacentre. Please refer to the EMR QMUL Safe Haven hosting agreement for more information. Back-up of the database is described in detail in the EMR QMUL Safe Haven hosting agreement.

Access to the eCRF will be via an encrypted and password (multi-factor authentication (MFA)) protected link (SSL encryption). Only persons on the delegation log (site, central or Sponsor) will be given the appropriate access to the database.

The co-ordinating site will not hold any patient identifiable data. All clinical data will be stored in an encrypted format on the database, only viewable in a readable format by local trial staff and only for participants recruited at their site.

#### **15.4 Transferring and transporting data**

All data will be handled in accordance with the Data Protection Act (2018) and GDPR. No patient identifiable data will leave each hospital site. All data will be transferred from recruiting sites to the trial coordinating office as described previously.

#### 15.5 Data Management

Immediate data cleaning will be performed following completion of the screening visit (visit 1) and biopsy visit (visit 2) of all data points prior to randomisation by the Trial Coordinating office. The subsequent data points will be regularly data cleaned throughout the trial. At the end of the trial, a final data clean will be performed and the PI will be required to sign -off to confirm the data is correct prior to database lock. The data cleaning, database lock and data export process is described in the Data Management Plan.

## **16.0 Confidentiality and De-identification of participants**

The Chief Investigator will be the data custodian for all data generated during the study.

The Chief Investigator and the study team will ensure that all participants' identities are protected at every stage of the study. To ensure this, at time of consent each participant will be allocated a unique screening number by database before undergoing any screening procedures.

The Principal Investigator is responsible for protecting the identity of participants at their site. Participants will be referred to only by their unique study identifier whenever data is transferred outside of the site, and in all correspondence between the site and the coordinating centre, co-investigators, sponsor, or anyone associated with the study. An enrolment log will be kept in the investigator site file at each recruiting site to link the unique identifier to the patient.

Initials and year of birth only will be collected on the eCRF and in this patient population will not be considered identifiable data.

No participants will be individually identifiable from any publications resulting from the study.

Information regarding study participants will be kept confidential and managed in accordance with the Data Protection Act (2018), the UK Policy Framework for Health and Social Care and

Research Ethics Committee approval. All study data will be stored in line with the Medicines for Human Use (Clinical Trials) Regulations 2004 and subsequent amendments and the Data Protection Act. Study data will be archived in line with the Medicines for Human Use (Clinical Trials) Regulations 2004 and all subsequent amendments, and as defined in the JRMO SOP 20 Archiving.

Patients will be consented and will not own the results generated using the sample/s and data collected and in addition will not be entitled to any interest in or share of any profit that might arise from research using the sample/s or data.

## 17.0 Monitoring, Audit, and Inspection

#### 17.1 Monitoring

A Trial Monitoring Plan will be developed and agreed by the sponsor and Chief Investigator based on the sponsor's risk assessment, which will include on site monitoring. Monitoring will be performed by the delegated personell within the EMR clinical team for the UK and EU sites. Monitor will be unblinded to the treat allocation. Monitoring procedures are detailed in the Trial Monitoring Plan.

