# 7.4 Blinding

Neither the participant nor any of the investigators or site staff who are involved in the treatment or clinical evaluation and monitoring of the participants will be aware of the study intervention received.

- The study drug and placebo will be provided in blinded treatment kit numbers obtained through the Early RA 3TR Database. Abatacept 125 mg and placebo matching will be provided in identically matched prefilled syringes that are visually indistinguishable. Syringes and boxes will be labelled with a kit number.
- Unblinded personnel will include designated representative(s) from the Sponsor or QMUL-designed personnel to review unblinded data.
- Blinded personnel will include designated representative(s) from the study site, and Sponsor. Administration of the study drug will be completed by blinded study site personnel. The study drug will be administered in the same manner to maintain the blindness of the treatment allocation.

The randomization code should not be broken except in medical emergencies when the appropriate management of the participant requires knowledge of the treatment randomization. The investigator documents and reports the action to the Sponsor, without revealing the treatment given to the participant to the Sponsor staff.

The Sponsor retains the right to break the code for SAEs that are unexpected and are suspected to be causally related to an investigational medicinal product and that potentially require expedited reporting to regulatory authorities. Randomization codes will not be broken for the planned analyses of data until all decisions on the evaluability of the data from each individual participant have been made and documented.

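### Section 17.1 unblinds the monitor, a member of the EMR clinical team, to treatment with no stated reason, and no monitoring task in the protocol needs the code

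*Protocol*

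**What the plan says.** Section 17.1 of the protocol provides for on-site monitoring under a Trial Monitoring Plan and names who does it: "Monitoring will be performed by the delegated personell within the EMR clinical team for the UK and EU sites". It then fixes that person's status: "Monitor will be unblinded to the treat allocation". No reason follows, and nothing limits the role to drug matters.

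The same group has other functions. Section 15.3 refers to the "central coordinating centre at EMR". The EMR laboratory runs the synovial gene-expression assay (section 9.5.2). The coordinating office raises manual queries (section 14.13) and cleans the data throughout the trial (section 15.5).

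Section 7.4 describes the blind. It covers "Neither the participant nor any of the investigators or site staff who are involved in the treatment or clinical evaluation and monitoring of the participants". Study drug comes in "identically matched prefilled syringes that are visually indistinguishable", and "Syringes and boxes will be labelled with a kit number". Section 7.4 adds: "Administration of the study drug will be completed by blinded study site personnel". It also allows some unblinded sponsor or QMUL representatives for reviewing unblinded data, without naming the monitor.

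**The concern.** An unblinded monitor is usually accepted where drug has to be prepared, or accounted for, in unblinded form. That monitor is then kept away from outcome data. Neither condition is visible here. The drug supply is arranged so that nobody at the site needs the code, yet a person from the coordinating team holds it and visits the sites.

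CDAI consists of two 28-joint counts and two global visual analogue scores (section 7.6.4), with no laboratory component. Such ratings can be nudged by conversation or by the way a query is put. Adverse event judgements are open to the same influence.

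What is at stake is mainly the comparison of abatacept minus placebo between biomarker groups. That contrast is secondary, but the interpretation of the trial leans on it. Section 14.1 reports a 10-point difference in delta CDAI between biomarker groups in an earlier cohort treated with methotrexate and no abatacept. A difference between Groups 1 and 3 alone therefore cannot tell a marker of abatacept response from a marker of general prognosis. The placebo-controlled contrast is the one that can.

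**Working it through.** No arithmetic applies: no figure in the protocol changes with the monitor's blinding status. The check is whether any task stated in the protocol requires the monitor to know the arm, and then which comparisons the knowledge could reach.

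**Step 1. Does a stated task need the code?**

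| Task | Section | Code needed? |
|---|---|---|
| Verify pharmacy accountability before disposal at site (given to the monitor) | 11.5 | No. Records are packs received and dispensed, participant, batch, expiry and quantity returned |
| Confirm that the kit dispensed is the kit the database allocated | 7.3, 7.4 | No. Kit number suffices |
| Confirm that the kit matches the patient's arm | 7.3 | Yes, but the protocol does not give this to the monitor, and it can be done centrally |
| Oversee administration | 7.4 | No. Staff who give the drug are blinded |
| Access to source records | 15.1 | No |
| Emergency unblinding | 7.4.1 | Done by the investigator or delegate through the database |
| Unblinding for SUSAR reports | 12.6.2 | Done by the sponsor's research office, with IT as backup |

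Only the third row needs the code, and it does not need to be done by the person who visits sites.

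**Step 2. What could the monitor's knowledge touch?** Section 15.1 gives sponsor representatives direct access to source data for monitoring, and the listed sources include medical records and patient questionnaires. That the monitor checks outcome data is a fair inference from this; the protocol does not list what is verified.

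**Step 3. Which comparisons are exposed?**

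- *Primary (section 14.7), Group 1 against Group 3.* Every patient is on abatacept. Knowing the arm gives no reason to favour either group. Biomarker class would have to be known as well.
- *Secondary (sections 2.2 and 14.8), Group 1 minus Group 2 against Group 3 minus Group 4.* Each difference sets abatacept against placebo, so knowledge of the arm can bear on both. Influence equal in the two biomarker groups would cancel in the final contrast; unequal influence would not.
- *Safety (section 14.9).* Summaries by treatment depend on event assessments, which knowledge of the arm can colour.

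**Step 4. For how long?** Section 7.7 unblinds each patient at the end of week 16, sends an email to the QMUL trial team and has the investigator enter the arm on the e-CRF. The protection at issue therefore concerns weeks 0 to 16 of each patient's participation.

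**The case against.** The strongest reply is that this is a disclosed choice. Section 7.4 defines the blind around participants, investigators and site staff, and allows some unblinded sponsor or QMUL personnel. That stands. A reader might infer a flat contradiction between 7.4 and 17.1, partly because 7.4 mentions monitoring of participants. The documents do not support this: that phrase concerns investigators and site staff, and the trial monitor is neither.

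Second, the Trial Monitoring Plan is not shown and may split drug monitoring from outcome monitoring. That is possible. But the protocol itself has fixed the status without a reason or a limit, and the text should be sound as it reads.

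Third, the leakage route is indirect and partly controlled. A blinded assessor does the joint counts and the physician global score (sections 7.2 and 7.5.4), patients mark their own scales (section 7.6.5), data changes require a reason (section 14.13), and the database keeps an audit trail (section 15.3). No section says that the monitor speaks with the assessors or raises queries on CDAI. This stands and limits the severity.

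Fourth, a reader might infer that the whole primary endpoint is at risk because the monitor's team knows biomarker class. No section gives the monitor biomarker results. Section 9.7 holds sample results apart from the e-CRF, open only to delegated laboratory and coordinating staff, and 17.1 unblinds to treatment alone.

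Finally, keeping the monitor blinded takes more than one sentence, because sections 7.7 and 12.6.2 also release or hold the allocation within the team. That is right, and the fix has to cover it.

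**Conclusion.** The point holds as an avoidable weakening of the double blind that is cheap to remove. It is neither a contradiction nor a demonstrated bias. Its size cannot be quantified from the protocol. The exposure is indirect, runs over weeks 0 to 16, and falls on the abatacept-versus-placebo contrasts by biomarker and on adverse event assessment. The primary comparison is affected only if biomarker class also becomes known to the monitor, which the protocol does not state.

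The conclusion rests on three assumptions: that the monitor sees outcome source data, inferred from section 15.1; that the unseen monitoring plan does not already separate the roles; and that section 7.4 governs what site staff know, although section 7.3 contains wording on the release of the randomisation result that could be read otherwise. The word in 17.1 may be a slip for blinded. The document does not settle this, and the correction would be the same.

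**What to change.** - In section 17.1, state that the monitor is blinded to treatment and to biomarker class until each patient's planned unblinding at the end of week 16 (section 7.7).
- State that the monitor checks drug accountability by kit number against the dispensing records, and that any kit-to-arm check is run centrally by someone already unblinded.
- State that the clinical-team member who keeps unblinded records under section 12.6.2 does not monitor outcome data.
- In section 7.4, list the monitor among the blinded personnel so that it agrees with 17.1.
- If there is a reason for an unblinded monitor, give it, and restrict that person to drug accountability, apart from whoever verifies outcome data and raises queries.

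The cost is short edits to sections 7.4, 12.6.2 and 17.1 and to the monitoring plan. Kit-to-arm reconciliation moves to a central unblinded role. Access to the e-CRF allocation field and to the week-16 unblinding email has to be set so that the monitor does not see an arm early. Sample size and data collection do not change, and the same monitor can continue. One limit remains: verification of a patient's data after that patient's code has been released is not protected.

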### 17.2 Auditing

The sponsor retains the right to audit any aspect of the study, study sites, or central facilities. In addition, any part of the study may be inspected by the regulatory bodies, and funders where applicable.

All sites and vendors are asked to inform the sponsor if notified of any Audit or inspection affecting this study.

## **18.0 Compliance**

The CI will ensure that the protocol and study is conducted in compliance with the principles outlined in the Medicines for Human Use (Clinical Trials) Regulations 2004 and subsequent amendments, current UK Policy Framework for Social and health care research (2017), GCP guidelines, the World Medical Association Declaration of Helsinki, the Sponsor's and study specific SOPs, and other regulatory requirements.

The study will not commence until sponsor permission to activate sites is received.

Sites will be individually activated by the CI and team; this will not occur until site approval is granted.

The procedures are compliant with the Ionising Radiation (Medical Exposure) Regulations, and appropriate review by a Medical Physics Expert and Clinical Radiation Expert has been undertaken.

#### **18.1 Non-Compliance**

All deviations from the study protocol will be recorded at the Trail Coordinating Office and appropriate action will be taken. Deviation forms will be requested from sites where deemed necessary by the trial manager.

Non-compliances may be captured from a variety of different sources including monitoring visits, CRFs, communications and updates. The sponsor will maintain a log of non-compliances to ascertain if there are any trends developing which need to be escalated.

#### 18.2 Notification of Serious Breaches to GCP and/or the protocol

A 'serious breach' is a breach which is likely to affect to a significant degree:

- The safety or physical or mental integrity of the participants of the study; or
- The scientific value of the study.

The site Principal investigator is responsible for reporting any potential serious breaches to the sponsor ([contact]) within **24 hours** of becoming aware of the event.

The Chief Investigator is responsible for reporting any potential serious breaches to the JRMO ([contact]) within 24 hours of becoming aware of the event.

The sponsor is responsible for determining whether a potential serious breach constitutes a serious breach, and will work with the CI to investigate and notify and report to the MHRA and REC (as applicable) within 7 working days of becoming aware of the serious breach.

#### EU sites

It is the responsibility of the lead site in each country to prepare and submit local forms to report Serious Breaches to their local ethical and regulatory bodies, as directed by the Sponsor.

## **19.0 Declaration of interests**

TSC members are required to declare any competing interests and complete a competing interests declaration form.

### 20.0 Peer review

A scientific peer review has been conducted by IMI at the grant application stage of this project.

## 21.0 Public and Patient Involvement (PPI)

This study design and protocol outline were presented to PM-PAG (Precision Medicine Patient Advisory Group) during the protocol writing stage. The PM-PAG were also involved in the review of patient facing documents. There is a plan to ensure patients are involved throughout the duration of the study. In addition to a PPI group organised by the Chief Investigator, there will be an overarching 3TR PPI group.

## 22.0 Indemnity/ Insurance

The insurance that Queen Mary University of London has in place provides cover for the design and management of the study as well as "No Fault Compensation" for participants, which provides an indemnity to participants for negligent and non-negligent harm.

## 23.0 Study committees

#### 23.1 Trial Management Group (TMG)

The Trial Management Group will include individuals responsible for the day-to-day management of the trial, such as the Chief Investigator, Statistician, Trial Manager, Research Nurse and Data Manager. The role of the group is to monitor all aspects of the conduct and progress of the trial, ensure that the protocol is adhered to and take appropriate action to safeguard participants and the quality of the trial itself. The TMG will meet monthly.

#### 23.2 Trial Steering Committee (TSC)

The role of the Trial Steering Committee (TSC) will be to provide overall supervision on behalf of the Trial Sponsor and Trial Funder and to ensure that the trial is conducted to GCP and the relevant regulations. In particular, the TSC will concentrate on the progress of the trial, e.g. recruitment, adherence to protocol, patient safety and the consideration of new information of relevance to the research question. The TSC will be asked to comment in detail on extension requests or substantial changes to the protocol.

The TSC has membership from the TMG plus independent members, including the chair as detailed in the TSC terms of reference. The TSC membership is for the duration of the study. If any members leave the TSC, the CI (in collaboration with the TSC Chair and TMG) will provide replacements promptly for appointment by the chair.

Decisions about continuation or termination of the trial or substantial amendments to the protocol will be the responsibility of the Trial Steering Committee. The TSC will meet every 12 months during the recruitment phase of the study. The meetings may take the form of a teleconference or face to face meetings.

## 24.0 Publication and dissemination policy

#### 24.1 Publication

It is anticipated that the results will be published in peer reviewed journals. Any investigator involved with this study is obliged to provide the Sponsor with complete results and all data derived from the study on request. Authorship of the final manuscript(s), interim publications, or abstracts will be decided according to active participation in the study design, trial management group and accrual of eligible patients. No participant may present data from his/her centre separately from the rest of the trial results unless approved by the CI/3TR-PARTNER-RA management group and the Sponsor.

All publications will be sent to the JRMO prior to publication. The full study report will be accessible via ISRCTN or ct.gov or other suitable public website within one year of the End of the Trial notification.

